#### **Exclusion criteria**

Subjects must not meet any of the following exclusion criteria to be eligible for enrollment into the study:

1. Patients with Cushing's disease (biochemical evidence of hypercortisolism).
2. Patients with compression of the optic chiasm causing any visual field defect that requires surgical intervention
3. Diabetic patients with poor glycemic control as evidenced by HbA1c  $>8\%$
4. Patients who are hypothyroid or adrenally insufficient and not on adequate replacement therapy
5. Patients with symptomatic cholelithiasis and acute or chronic pancreatitis
6. Patients with risk factors for torsade de pointes, i.e. patients with a baseline QTcF  $>450$  ms in males, and  $>460$  ms in females

7. Hypokalaemia, hypomagnesaemia, uncontrolled hypothyroidism, family history of long QT syndrome or concomitant medications with known risk of Torsades de pointes (TdP). Drugs with possible risk of TdP should be avoided whenever feasible.
8. Patients who have congestive heart failure (NYHA Class III or IV), unstable angina, sustained ventricular tachycardia, clinically significant bradycardia, advanced heart block, history of acute MI less than one year prior to study entry or clinically significant impairment in cardiovascular function
9. Concomitant disease(s) that could prolong the QT interval such as autonomic neuropathy (caused by diabetes or Parkinson's disease), HIV, cirrhosis, uncontrolled hypothyroidism or cardiac failure
10. Patients with liver disease such as cirrhosis, chronic active hepatitis, or chronic persistent hepatitis, or patients with ALT/AST > 2.0 X ULN, serum bilirubin >2.0 X ULN
11. Presence of Hepatitis B surface antigen (HbsAg) or Hepatitis C antibody test (anti-HCV)
12. Patients with serum creatinine >2.0 X ULN
13. Patients with WBC <3 X 10^9/L; Hb 90% < LLN; PLT <100 X 10^9/L
14. Patients with the presence of active or suspected acute or chronic uncontrolled infection
15. Patients who have undergone major surgery/surgical therapy for any cause within 4 weeks prior screening
16. Patients with abnormal coagulation (PT and/or APTT elevated by 30% above normal limits) or patients receiving anticoagulants that affect PT (prothrombin time) or APTT (activated partial thromboplastin time)
17. History of syncope or family history of idiopathic sudden death
18. History of immunocompromise, including a positive HIV test result (ELISA and Western blot)
19. Sexually active males unless they use a condom during intercourse while taking drug and for 3 months following last dose of pasireotide and should not father a child in this period. A condom is required to be used also by vasectomized men in order to prevent delivery of the drug via seminal fluid.
20. Pregnant or nursing (lactating) women, where pregnancy is defined as the state of a female after conception and until the termination of gestation, confirmed by a positive urine pregnancy test
21. Women of child-bearing potential, defined as all women physiologically capable of becoming pregnant, unless they are using highly effective methods of contraception during dosing and 3 months following last dose of pasireotide. Highly effective contraception methods include:
  - Total abstinence (when this is in line with the preferred and usual lifestyle of the subject. Periodic abstinence (e.g., calendar, ovulation, symptothermal, post-ovulation methods) and withdrawal are not acceptable methods of contraception)
  - Female sterilization (have had surgical bilateral oophorectomy with or without hysterectomy) or tubal ligation at least six weeks before taking study treatment. In case of oophorectomy alone, only when the reproductive status of the woman has been confirmed by follow up hormone level assessment

- Male sterilization (at least 6 months prior to screening). For female subjects on the study the vasectomized male partner should be the sole partner for that subject
- Combination of any two of the following (a+b or a+c, or b+c):
  - a) Use of oral, injected or implanted hormonal methods of contraception or other forms of hormonal contraception that have comparable efficacy (failure rate <1%), for example hormone vaginal ring or transdermal hormone contraception.
  - b) Placement of an intrauterine device (IUD) or intrauterine system (IUS)
  - c) Barrier methods of contraception: Condom or Occlusive cap (diaphragm or cervical/vault caps) with spermicidal foam/gel/film/cream/vaginal suppository
- In case of use of oral contraception women should have been stable on the same pill for a minimum of 3 months before taking study treatment.
- Women are considered post-menopausal and not of child bearing potential if they have had 12 months of natural (spontaneous) amenorrhea with an appropriate clinical profile (e.g. age appropriate, history of vasomotor symptoms) or have had surgical bilateral oophorectomy (with or without hysterectomy) or tubal ligation at least six weeks ago. In the case of oophorectomy alone, only when the reproductive status of the woman has been confirmed by follow up hormone level assessment is she considered not of child bearing potential.

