#### Key Exclusion criteria

- Patients with Cushing's disease (biochemical evidence of hypercortisolism)
- Patients who require surgical intervention.
- HbA1c  $> 8\%$  at screening
- Known hypersensitivity to somatostatin analogues
- History of liver disease
- Symptomatic cholelithiasis or acute or chronic pancreatitis
- Cardiac or repolarization abnormality
- Life-threatening autoimmune disorders
- Inadequately treated adrenal or thyroid insufficiencies
- Inadequate bone marrow function

**Investigational therapy:** Pasireotide LAR

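### Exclusion 5 requires gallstones and pancreatitis together in section 3.2.1, but either one alone in the Protocol Summary; the hemoglobin limit in exclusion 13 also needs rewriting

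*Combined protocol and SAP*

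**What the plan says.** The full exclusion list in section 3.2.1 opens with "Subjects must not meet any of the following exclusion criteria to be eligible for enrollment into the study", so meeting any single item makes a patient ineligible. Section 3.2 (Study population) makes the investigator responsible for offering treatment only to patients who meet every inclusion criterion and no exclusion criterion.

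- **Item 5** of that list: "Patients with symptomatic cholelithiasis and acute or chronic pancreatitis". The Protocol Summary, under Key Exclusion criteria: "Symptomatic cholelithiasis or acute or chronic pancreatitis".
- **Item 13** gives three blood-count limits. White cells and platelets are each a plain less-than limit. The hemoglobin entry between them is printed as Hb 90% < LLN. The summary's nearest counterpart is "Inadequate bone marrow function", with no number.
- **Item 8** excludes congestive heart failure of NYHA Class III or IV. **Item 9** lists diseases that could prolong the QT interval and ends with "HIV, cirrhosis, uncontrolled hypothyroidism or cardiac failure", with no NYHA class.

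**The concern.** An exclusion criterion should give the same answer whoever applies it. Item 5 does not: a screener working from 3.2.1 and one working from the summary can reach opposite decisions on the same patient. The hemoglobin entry cannot be applied as printed without the screener supplying the intended inequality.

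The conditions matter for this drug on the protocol's own account. Section 1.2.1.1.1 reports cholelithiasis in 30.9% of the pasireotide LAR arm of one phase III acromegaly study. It also lists anemia and increased blood amylase among the adverse drug reactions. Pancreatitis itself is not on that list. What is at stake is whether a patient whom the summary regards as unsuitable could be treated under the literal text of 3.2.1.

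**Working it through.** This is a check of wording and logic. The plan gives no figure to reproduce on this point, and no power or sample-size input bears on it.

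**Item 5.** Let G be symptomatic cholelithiasis and P be acute or chronic pancreatitis.

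| Patient | 3.2.1 read literally (G and P) | Protocol Summary (G or P) | Agree? |
|---|---|---|---|
| G only | not excluded | excluded | no |
| P only | not excluded | excluded | no |
| G and P | excluded | excluded | yes |

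The texts disagree for two of the three patient types.

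Does anything else close the gap? No other item in 3.2.1 names gallstones or pancreatitis. The bilirubin limit in item 10 or the infection clause in item 14 might catch some such patients incidentally, but neither is a rule on these conditions. The visit schedule has a gallbladder ultrasound at V1, but no exclusion is tied to its result.

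Can *and* be presumed to mean *or*? Usage elsewhere in the list does not settle it. Items 8, 9 and 10 use *or* for alternatives, item 16 uses *and/or*, and item 4 uses *and* for a true conjunction (insufficient and not adequately replaced).

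Can the summary be presumed to govern? The documents state no rule of precedence, and the two lists differ elsewhere. The age range is 18–70 in the summary and 18–80 in 3.2.1, and the summary's exclusion for life-threatening autoimmune disorders has no counterpart in 3.2.1.

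**Item 13.** The documents give no lower limit of normal (LLN) for hemoglobin. Assume 12.0 to 13.5 g/dL for illustration. The printed expression can be parsed in three ways:

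1. Hb below 90% of LLN: 0.90 × 12.0 = 10.8; 0.90 × 13.5 = 12.15 g/dL.
2. 90% of Hb below LLN: 12.0 / 0.90 = 13.3; 13.5 / 0.90 = 15.0 g/dL.
3. Hb 90% below LLN: 0.10 × 12.0 = 1.2; 0.10 × 13.5 = 1.35 g/dL.

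Reading 3 is physiologically implausible. Reading 2 puts the cut-off above the LLN itself, so it would exclude people with normal hemoglobin. Reading 1 fits the two neighboring lower limits and the summary's reference to bone marrow function. It is the likely intent, but it has to be inferred.

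**Items 8 and 9.** Exclusions combine as a union.

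- NYHA III–IV: excluded by item 8.
- NYHA I–II: not caught by the heart-failure clause of item 8. In "uncontrolled hypothyroidism or cardiac failure", if *cardiac failure* stands unqualified, item 9 excludes these patients and the class limit in item 8 has no effect. If *uncontrolled* governs both nouns, controlled NYHA I–II is not excluded by item 9.

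**The case against.** The strongest reply on item 5 is that a phrase of the form *patients with X and Y* can loosely list two excluded groups, which would match the summary. That stands as a possible reading. It means one cannot say outright that the trial admits patients with pancreatitis alone, only that the literal 3.2.1 text does not exclude them. It does not remove the contradiction.

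Four stronger inferences are tempting, and the documents do not support them.

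- **That the hemoglobin rule has no usable meaning, or could bar a sizeable share of healthy people.** One reading is clearly more plausible than the others. If healthy values are normal with LLN = mean − 1.96 SD and a coefficient of variation of 6–8%, a cut-off of LLN / 0.90 would exclude about 37% to 22%. That rests on the unlikely reading 2 and on distributional values absent from the documents. Under reading 1, the same assumptions give about 0.03% to 0.13%.
- **That items 8 and 9 fail when applied.** They can be applied together. The worst that follows is redundancy or unclear scope, and overlap is not unusual in this list: cirrhosis appears in both items 9 and 10. No patient is shown to be wrongly admitted.
- **That pre-existing disease would be counted as a drug reaction, shifting an adverse-event rate by 10 percentage points (1/10).** Section 3.4.2 counts conditions present before treatment as adverse events only if they worsen or become more frequent, and has each event assessed for relationship to the drug. The 10 points are what any single event contributes among ten patients; they do not measure this defect. What remains is the possible entry of a patient whose pre-existing disease could worsen on treatment.
- **That the stricter version of item 5 must be the right one.** The documents show that the two texts conflict, not which was intended.

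**Conclusion.** Exclusion 5 is wrong as written: the list that governs entry and the summary give opposite answers for gallstones alone and for pancreatitis alone, and nothing else in 3.2.1 resolves it. This rests on the literal reading of *and* and on section 3.2 making the listed criteria decisive.

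The hemoglobin limit in exclusion 13 is a drafting error with one likely meaning that the text does not state. The relation between items 8 and 9 is a minor wording matter.

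How many patients would be affected cannot be estimated, since the documents give no prevalence of these conditions in the recruitment pool. The POMC endpoint, the sample of 10 and the stated power above 90% do not depend on any of this. The point should be corrected because it bears on safety eligibility and the remedy is cheap.

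**What to change.** Make one short amendment to the eligibility text.

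1. Reconcile exclusion 5 in section 3.2.1 with the Protocol Summary so that both give the same answer for each condition alone and for the two together. The sponsor confirms the intended rule.
2. Rewrite the hemoglobin limit in exclusion 13 as a single inequality against the laboratory's lower limit of normal, with the intended limit confirmed by the sponsor.
3. As a minor clarification, state how *cardiac failure* in item 9 relates to the NYHA III–IV limit in item 8, and whether *uncontrolled* applies to it.
4. Apply the corrected list to all screened patients.

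The cost is the amendment and its IRB approval. The blood count and gallbladder ultrasound are already scheduled at V1, so no new test is needed. Depending on the rule confirmed, an occasional patient may be screened out, which is noticeable in a study of ten but does not alter its design.

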### 3.3. Treatment

#### 3.3.1. Investigational Therapy

Patients who have provided written informed consent will undergo screening procedures. Once eligibility is established patients will begin therapy with Pasireotide LAR 40 mg.

Pasireotide LAR 40 mg will be administered as intra-muscular (i.m.) intragluteal injections every 4 weeks. Uptitration will occur to Pasireotide LAR 60 mg after 6 months of therapy with Pasireotide LAR 40 mg if POMC level has not been suppressed and/or pituitary tumor shrinkage has not occurred. For patient receiving 40 mg dose down-titration to 20 mg is permitted for patients who do not tolerate 40 mg. For patients who are up-titrated to the 60 mg dose down-titration to 40 mg is permitted if tolerability issues occur on this higher dose.

Medication labels will comply with legal requirements and be printed in English. The storage conditions for study drug will be described on the medication label.

Should anti-diabetic treatment be needed during the study (see adverse events) this will be provided by the investigator according to standard clinical practice for diabetes care. The order of initiation of anti-diabetic therapy is expected to be, but is not prescribed as part of this protocol:

- Metformin at individual doses starting from 1000 mg/day to maximum dose according to the approved package insert and depending on the patient tolerability
- Sitagliptin 50 or 100 mg administered orally once a day

- Insulin administered s.c. according to package insert

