### 3.3.2. Concomitant therapy

Chronic maintenance medications will continue on their current therapy during the course of the study. The patient will be told to notify the investigational site about any new medications he/she takes after the start of the study drug. Any changes in the dose of any medication the patient was taking prior to or during the study have to be notified as well. All medications (other than study drug) and significant non-drug therapies (including physical therapy and blood transfusions) administered during the study will be documented in the subject records.

The use of drugs that may stimulate GH secretion such as L-dopa or arginine is not permitted. In addition, the use of the drugs listed in the exclusion criteria is not permitted.

Limited published data indicate that somatostatin analogs might decrease the metabolic clearance of compounds known to be metabolized by cytochrome P450 enzymes, which may be due to the suppression of growth hormones. Since it cannot be excluded that pasireotide may have this effect, other drugs mainly metabolized by CYP3A4 and which have a low therapeutic index (e.g., quinidine, terfenadine) should therefore be used with caution. Consumption of fruits that may inhibit the CYP3A4 system (star fruit, papaya, pomegranate and grapefruit) will also be advised against during the study.

Somatostatin analogs have been associated with alterations in nutrient absorption, so pasireotide may have an effect on absorption of orally administered drugs. Concomitant administration with cyclosporine may decrease blood levels of cyclosporine and result in transplant rejection.

Patients receiving insulin, oral hypoglycemic agents, beta-blockers, calcium channel blockers, or agents to control fluid and electrolyte balance, may require dose adjustments of these therapeutic agents. Any anti-diabetic medications that the patient takes during the study will be listed in study-specific source documents. If oral contraception is used, the patient must have been practicing this method of birth control for at least three months prior to enrollment and must agree to continue the oral contraceptive throughout the course of the study and for 3 months after pasireotide LAR last dose.

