#### Prohibited concomitant medications

The use of concomitant medication with a known risk of Torsades de Pointes (TdP) is prohibited. In case a patient needs to take medication with a known risk of TdP, it will require study drug discontinuation prior to starting the medication. Appendix 1 lists QT prolonging medications.

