#### Interruption or discontinuation of treatment

Patients who experience an enlargement of their pituitary tumor or any clinical signs consider to represent progression of the tumor while on Pasireotide LAR therapy will be withdrawn from the study by the investigator. Patients that experience severe or life-threatening hyperglycemia (diabetic ketoacidosis, hyperosmolar coma), develop jaundice, hepatitis or other primary hepatic dysfunction will be discontinued from the study. Patients who develop an allergic reaction to Pasireotide LAR® Depot will be discontinued. It will be documented whether or not each patient completed the clinical study. If for any patient either study treatment or observations were discontinued the reason will be recorded. Reasons that a patient may discontinue participation in a clinical study are considered to constitute one of the following:

1. adverse event(s)
2. abnormal laboratory value(s)
3. abnormal test procedure result(s)

4. subject's condition no longer requires study treatment
5. protocol violation
6. subject withdrew consent
7. lost to follow-up
8. administrative problems
9. death

Any patient who receives at least one dose of trial medication will be included in the safety analysis.

	V1	V2	V3	V4	V5	V6	V7	V8	V9	V10	V11	V12	V13	V14	V15
OGTT (75 gm)		X					X							X	
CBC (w/ WBC differential)	X			X			X			X				X	
Hepatic Function Panel (AST, ALT, Bilirubins, AlkPhos)	X			X			X			X				X	
Basic Metabolic Panel (Na, K, Cl, HCO 3 , BUN, Cr, Ca)	X			X			X			X				X	
Serum Cortisol	X	X	X	X	X	X	X	X	X	X	X	X	X	X	
Plasma POMC	X	X	X	X	X	X	X	X	X	X	X	X	X	X	
Plasma ACTH	X	X	X	X	X	X	X	X	X	X	X	X	X	X	
Thyroid Panel (Free T4, TSH)	X														
Coagulation (PT, PTT)	X						X							X	
Serum & Plasma Bank	X	X	X	X	X	X	X	X	X	X	X	X	X	X	
Urinalysis	X							X						X	
Urine Pregnancy	X														
24 Hr Urinary Free Cortisol and Creatinine	X														
Salivary Cortisol (late night)(x5)	X							X						X	
Pituitary MRI w/ contrast	X							X						X	
Gallbladder Ultrasound and reading	X													X	
12 Lead ECG and reading	X	X	X	X			X			X				X	

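### The visible visit table schedules a pregnancy test only at V1, although up to 12 four-weekly depot injections may follow

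*Combined protocol and SAP*

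**What the plan says.** **Entry and contraception (3.2.1).** Exclusion 20 bars pregnant or nursing women and defines pregnancy as lasting "until the termination of gestation, confirmed by a positive urine pregnancy test". Exclusion 21 bars women of child-bearing potential "unless they are using highly effective methods of contraception during dosing and 3 months following last dose of pasireotide". The list opens with "Subjects must not meet any of the following exclusion criteria to be eligible for enrollment into the study". Section 3.3.2 adds that a woman on oral contraception "must agree to continue the oral contraceptive throughout the course of the study and for 3 months after pasireotide LAR last dose".

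**Dosing (3.3.1 and 3.1).** "Pasireotide LAR 40 mg will be administered as intra-muscular (i.m.) intragluteal injections every 4 weeks", with the last at Week 44.

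**Testing (visit table, after the text on interruption or discontinuation of treatment).** The row labelled "Urine Pregnancy" has one mark, at V1.

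**Stopping.** The plan states several stop rules outright. Patients who "develop jaundice, hepatitis or other primary hepatic dysfunction will be discontinued from the study", and if a patient needs a drug with a known torsades risk, "it will require study drug discontinuation prior to starting the medication". Other rules cover tumour growth, severe hyperglycaemia, allergy, persistent grade 3 or higher drug-related events, QTcF, liver tests and uncontrolled diabetes. None names pregnancy. Section 3.4.3 requires a pregnancy to be reported on an SAE form and followed to outcome, and gives no instruction on dosing.

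**The concern.** The plan sets demanding contraceptive requirements for the whole dosing period and 3 months beyond it, but its visible schedule checks pregnancy status once, at V1. Contraception can fail. With a long-acting intramuscular depot, the useful moment to find a pregnancy is before the next injection, because stopping afterwards does not remove the dose already given. What is at stake is avoidable fetal exposure to repeated injections. This is a participant-safety point and does not touch the POMC or tumour-volume analyses.

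**Working it through.** The plan states no figure to reproduce here. The check is a count of table marks against dosing visits.

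**Inputs**
- Pregnancy test row: marked at V1 only.
- Urinalysis row and pituitary MRI row: each marked at V1, V8 and V14.
- Dosing interval: 4 weeks (3.3.1). Last injection: Week 44 (3.1).
- MRI timing: baseline, 6 months and 12 months (3.1).
- Safety follow-up: 8 weeks after the final study visit (3.4.2).
- Half-life of the LAR formulation: about 16 days (1.2.1.1.1).
- Planned enrolment: 10 patients (3.1). Number of women of child-bearing potential: not given, so 0 to 10.
- First injection at Week 0: an assumption, since the visible text does not state the week.

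**Step 1: number of injections.** 44/4 + 1 = 12, at Weeks 0, 4, ..., 44. If the first were at Week 4 there would be 11, so 12 is an upper figure.

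**Step 2: match visits to weeks.** Taking V2 as Week 0 and four-weekly visits, V8 is 4 × 6 = Week 24, V13 is 4 × 11 = Week 44 and V14 is 4 × 12 = Week 48. V8 and V14 are where the 6- and 12-month MRIs are marked. V15 is then 48 + 8 = Week 56.

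**Step 3: tests against injections.** Tests at V1: 1. Tests at V2 to V15: 0. On the Step 2 mapping the injection visits are V2 to V13, so 0 of 12 has a pregnancy test, including the first.

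**Step 4: sensitivity to the mapping.** The OGTT and coagulation rows have their mid-study mark at V7, not V8. If that meant V7 = Week 24, V1 would be Week 0 and the one test would fall at the first injection, leaving 12 − 1 = 11 of 12 without one. This sits badly with 3.3.1, where screening comes before dosing. The single-test count is the same on either reading.

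**Step 5: would a lighter schedule do?** Adding the test only where urinalysis is repeated (V8 and V14) would, on the Step 2 mapping, still allow the injections at V2 to V7, which is 6, before the first repeat test.

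**Step 6: why before the injection.** By simple half-life arithmetic, the fraction left 28 days after an injection is 2^(−28/16) = 2^(−1.75), about 0.30. This is illustrative only; it shows that exposure continues past the dosing interval.

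**Step 7: added tests.** 12 injection visits + V15 = 13 per woman. Over 0 to 10 women the total is 0 to 13 × 10 = 130.

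**The case against.** **Unseen text.** The top of the visit table, its week labels, any footnotes and the text of 3.4.1 are not visible, and the consent pages were removed. A retest instruction could be there. This stands as a limit on confidence. Against it, the pregnancy row itself is intact, and neighbouring rows show repeat marks where repeats are intended.

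**The criteria may reach beyond entry.** Section 3.2 says only patients meeting none of the exclusions are offered treatment, and 3.3.2 carries the excluded drugs into the treatment period. The first can still be read as a rule about entry. Even on the wider reading it schedules no test, so a new pregnancy could go unnoticed.

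**Other safeguards.** Monthly examination, questioning about adverse events and the Sponsor-Investigator's event review (3.4.4) may raise suspicion. None is a scheduled pregnancy test.

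**Contraception is strict.** Apart from abstinence or sterilisation, two combined methods are required. That lowers the risk but does not remove it, and there may be no eligible women of child-bearing potential at all. Frequency of retesting is partly a judgement, but Step 5 shows what a sparser schedule leaves open.

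**Two stronger readings are not supported.**
- A reader might infer that dosing could properly continue in a known pregnancy. It could not reasonably: exclusion 20 and the Sponsor-Investigator's review give a clear basis to stop, and the listed discontinuation reasons, though permissive, offer a route. What is missing is an explicit mandatory sentence.
- A reader might infer a reporting gap from the 8-week SAE minimum against 3 months of contraception. Section 3.4.3 sets no time limit on pregnancy reporting, and 3.4.4 says at least 8 weeks and still takes later SAEs of suspected causality.

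**Conclusion.** The concern holds for detection. In the visible schedule there is one pregnancy test, at V1, and none at V2 to V15. On the mapping that fits the MRI marks, none of the 12 injections has a test at its own visit. A pregnancy beginning after V1 would not be found by any scheduled test before the next injection. The absent stop sentence is a supporting clarification, not a separate defect.

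The count of 12 assumes a first dose at Week 0. The visible text gives no reproductive-toxicity data, so harm per exposure cannot be sized. Confidence is medium because parts of the schedule are not visible. The change is worth making because it is specific and cheap, and no efficacy or power result depends on it.

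**What to change.** 1. In the visit table, for women of child-bearing potential, mark the existing urine pregnancy test before dosing at every injection visit, including the first, and at the V15 follow-up.
2. In the text on interruption or discontinuation of treatment, add one supporting sentence: a positive pregnancy test stops further injections and the patient is followed for safety.

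**Cost.** The tests counted in Step 7 use visits that already take place. One amendment needs IRB approval, since section 5.1 lists adding a safety-monitoring test among the changes that require it, and the consent form probably needs an update. If the unseen part of the schedule already requires retesting, only the stop sentence would remain to be added.
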